12.3.4.3 Electrocardiogram

For the treatment-emergent ECG measurements, a summary of observed values and change from baseline values will be provided, at each scheduled visit and time point, as applicable, for the following ECG interval measurements (in msec): RR, PR, QT, and QT interval corrected by Fredericia's formula (QTcF), QRS duration, and heart rate (HR) (beats per minute).

The number and percentage of subjects meeting a threshold analysis criterion during the TE Period will be summarized. The threshold analysis criteria will be provided in the SAP.

12.3.4.4 Vital Signs

For the treatment-emergent vital signs measurements, the observed values and change from baseline values will be summarized at each scheduled visit. The following vital signs parameters will be summarized: systolic and diastolic blood pressure (mm Hg), body temperature (°C), pulse rate (heart rate, beats per minute), and respiratory rate (breaths per minute).

The number and percentage of subjects meeting a threshold analysis criterion during the TE Period will be summarized. The threshold analysis criteria will be provided in the SAP.

12.3.4.5 Pulse Oximetry

For the treatment-emergent pulse oximetry measurements, a summary of observed values and change from baseline values will be provided at each scheduled visit for the percent of oxygen saturation by pulse oximetry.

The number and percentage of subjects with shift changes from baseline (normal/missing and low according to the reference range) to the lowest percent of oxygen saturation during the TE Period will be summarized.

12.3.4.6 Ophthalmologic Examinations

The ophthalmologic examination results will be presented in individual subject data listings.

12.3.4.7 Physical Examination

PE findings will be presented in an individual subject data listing only.

12.4 Interim Analysis

Not applicable.

12.5 Data Monitoring Committee Analysis

The DMC (Section 9.1.7) will conduct periodic planned safety review(s) of study data. Details of the safety and efficacy review(s) will be described in the DMC Charter.

12.6 Clinical Pharmacology Analysis

12.6.1 Pharmacokinetic Analysis

The PK analysis of ELX, TEZ, IVA, and relevant metabolites may be performed using nonlinear mixed effects modeling and/or standard noncompartmental analysis, as data allow. Metabolites may be included in the analyses as supported by data. Descriptive statistics will be used to summarize PK parameter values for all analytes.

A detailed description of the planned PK analysis will be presented in the CPAP.

12.6.2 Pharmacokinetic/Pharmacodynamic Analyses

PK/PD analyses may be performed on selected PD assessments, which include SwCl, LCI_{2.5}, as well as other endpoints such as [REDACTED]

A sequential approach will be used to perform the population PK/PD analysis. The Bayesian estimates of individual PK parameters from the final population PK model will be used to simulate PK profiles for each subject. The simulated ELX, TEZ, IVA, or metabolite plasma concentrations will be used in the potential pharmacological response models to describe changes in each endpoint. Fixed- and random-effect parameter estimates and their uncertainty will be estimated.

13 PROCEDURAL, ETHICAL, REGULATORY, AND ADMINISTRATIVE CONSIDERATIONS

13.1 Adverse Event and Serious Adverse Event Documentation, Severity Grading, and Reporting

13.1.1 Adverse Events

13.1.1.1 Definition of an Adverse Event

An AE is defined as any untoward medical occurrence in a subject during the study; the event does not necessarily have a causal relationship with the treatment. This includes any newly occurring event or worsening of a pre-existing condition (e.g., increase in its severity or frequency) after the ICF is signed.

An AE is considered serious if it meets the definition in Section [13.1.2.1](#).

13.1.1.2 Clinically Significant Assessments

Study assessments including laboratory tests, ECGs, PEs, and vital signs will be assessed and those deemed to have clinically significant worsening from baseline will be documented as an AE. When possible, a clinical diagnosis for the study assessment will be provided, rather than the abnormal test result alone (e.g., urinary tract infection, anemia). In the absence of a diagnosis, the abnormal study assessment itself will be listed as the AE (e.g., bacteria in urine or decreased hemoglobin).

An abnormal study assessment is considered clinically significant if the subject has 1 or more of the following:

- Concomitant signs or symptoms related to the abnormal study assessment
- Further diagnostic testing or medical/surgical intervention
- A change in the dose of study drug or discontinuation from the study

Repeat testing to determine whether the result is abnormal, in the absence of any of the above criteria, does not necessarily meet clinically significant criteria. The determination of whether the study assessment results are clinically significant will be made by the investigator.

A laboratory value that is Grade 4 will not automatically be an SAE. A Grade 4 laboratory value will be an SAE if the subject's clinical status indicates a life-threatening AE.

13.1.1.3 Documentation of Adverse Events

All AEs will be collected from the time the ICF is signed until the following times:

- For subjects who do not enroll: until time of screen failure (e.g., screen failure, withdrawal of consent)
- For enrolled subjects who have a Safety Follow-up Visit: through the Safety Follow-up Visit
- For enrolled subjects who do not have a Safety Follow-up Visit, the earliest of
 - o 28 days after the last dose of study drug, or
 - o the ETT Visit, if that visit is 3 weeks or later following the last dose of study drug (see Section [9.1.4](#))

All subjects' parents or legal guardians will be queried, using nonleading questions, about the occurrence of AEs at each study visit. When possible, a constellation of signs and/or symptoms will be identified as 1 overall event or diagnosis. All AEs for enrolled subjects will be recorded in the CRF and source document. AEs for subjects who are screened but not subsequently enrolled will be recorded only in the subject's source documents. The following data will be documented for each AE:

- Description of the event
- Classification of “serious” or “nonserious”
- Date of first occurrence and date of resolution (if applicable)
- Severity
- Causal relationship to study drug(s)
- Action taken
- Outcome
- Concomitant medication or other treatment given

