Standard 12-lead ECG	X		X			X			X	X	X	Performed before any other procedures that may affect heart rate (HR), such as blood draws, and in the supine position after the subject has been at rest for at least 5 minutes (Section 11.5.4).
Sweat chloride	X			X		X			X	X		Section 11.4.1
Multiple-breath washout	X			X		X			X	X		Performed in multiple replicates pre-bronchodilator in subjects ≥3 years of age at screening (Section 11.4.2).

Table 3-4 Study VX20-445-111, Part B Treatment Period and Safety Follow-up Visit

Event/ Assessment ^a	Day 1	Day 3 (± 1 day)	Day 15 (± 3 days)	Week 4 (± 5 days)	Week 8 (± 5 days)	Week 12 (± 5 days)	Week 16 (± 5 days)	Week 20 (± 5 days)	Week 24 (± 5 days)	ETT Visit	Safety Follow-up Visit (28 ± 7 Days After the Last Dose of Study Drug ^b)	Comments
Serum chemistry	X		X	X	X	X	X	X	X	X	X	Serum chemistry will be drawn prior to study drug dosing on Day 1. Liver function testing (ALT, AST, GGT, ALP, and total bilirubin) must be performed at the scheduled visits and at Week 20 (a minimum of every 4 weeks after Week 4). A local laboratory may be used for the Week 20 sample if a subject cannot return to the study site for the blood draw (Section 11.5.2).
Hematology			X	X ^c	X	X	X		X	X	X	Section 11.5.2
Coagulation									X	X	X	
Urinalysis	X								X	X		

^c It is recommended that subjects weighing <10.4 kg do not complete the Week 4 hematology blood draw.

Table 3-4 Study VX20-445-111, Part B Treatment Period and Safety Follow-up Visit

Event/ Assessment ^a	Day 1	Day 3 (± 1 day)	Day 15 (± 3 days)	Week 4 (± 5 days)	Week 8 (± 5 days)	Week 12 (± 5 days)	Week 16 (± 5 days)	Week 20 (± 5 days)	Week 24 (± 5 days)	ETT Visit	Safety Follow-up Visit (28 ± 7 Days After the Last Dose of Study Drug ^b)	Comments
Observation 4 hours after the AM dose	X											Section 9.6.1
Medications review	Continuous, From Signing of ICF Through Completion of Study Participation										Completion of study participation is defined in Section 9.1.6.	
Treatments and procedures review												
Adverse events	Continuous, From Signing of ICF Through Completion of Study Participation										Section 13.1; completion of study participation is defined in Section 9.1.6.	

Table 3-4 Study VX20-445-111, Part B Treatment Period and Safety Follow-up Visit

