9.1.3 Follow-up

The Safety Follow-up Visit is scheduled to occur 28 (± 7) days after the last dose of study drug. The Safety Follow-up Visit is not required for Part B subjects who complete the Week 24 Visit and enroll in the OLE safety study within 28 days after the last dose of study drug.

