9.1.4 Early Termination of Treatment

If a subject prematurely discontinues study drug treatment, an Early Termination of Treatment (ETT) Visit should be scheduled as soon as possible after the decision to discontinue treatment. Subjects who prematurely discontinue treatment will also be required to complete the Safety Follow-up Visit ([Table 3-2](#) for Part A and [Table 3-4](#) for Part B), if applicable (Section 9.1.3).

If the ETT Visit occurs 3 weeks or later following the last dose of study drug, then the ETT Visit will replace the Safety Follow-up Visit.

Subjects who prematurely discontinue study drug treatment will continue to complete all scheduled study visits for assessments following completion of the ETT Visit, as detailed in [Table 3-4](#).

If a subject withdraws from the study and also withdraws consent or assent, no further assessments will be performed. Vertex may retain and continue to use any data and samples collected before such withdrawal of consent or assent (Section 9.9).

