9.1.6 Completion of Study Participation

Completion of study participation for each individual subject is defined as 1 of the following:

Part A

- For subjects who complete the Treatment Period: the Safety Follow-up Visit
- For subjects who prematurely discontinue study drug treatment but do not withdraw consent (and assent, as applicable): the latest of the Day 15 Visit, ETT Visit, or Safety Follow-up Visit
- For subjects who withdraw consent or assent: date of withdrawal of consent or assent, whichever is earlier (Section 9.9)

Part B

- For subjects who complete the Treatment Period and enter an OLE safety study within 28 days of the Week 24 Visit: the Week 24 Visit
- For subjects who complete the Treatment Period and do not enter an OLE safety study within 28 days of the Week 24 Visit: the Safety Follow-up Visit
- For subjects who prematurely discontinue study drug treatment but do not withdraw consent (and assent, as applicable): the latest of the Week 24 Visit, ETT Visit, or Safety Follow-up Visit (if required)
- For subjects who withdraw consent or assent: date of withdrawal of consent or assent, whichever is earlier (Section 9.9)

If subjects are lost to follow-up (Section 9.1.5), the date of completion of study participation will be defined as the date of the last contact.

The end of study is defined in Section 13.2.9.

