13.1.2.2 Reporting and Documentation of Serious Adverse Events

All SAEs that occur after obtaining informed consent through the Safety Follow-up Visit, regardless of causality, will be reported by the investigator to Vertex Global Patient Safety (GPS) **within 24 hours of identification**. In addition, all SAEs that occur after the Safety Follow-up Visit and are considered related to study drug(s) will be reported to Vertex GPS **within 24 hours of identification**.

For SAEs that occur after obtaining informed consent through the Safety Follow-up Visit, the SAE Form will be completed for new/initial events as well as to report follow-up information on previously reported events. Investigators are asked to report follow-up information as soon as it becomes available to ensure timely reporting to health authorities.

Please send completed SAE Forms to Vertex GPS via:

Email: [REDACTED] (preferred choice)

Fax: [REDACTED]

For technical issues related to submitting the form, contact telephone: [REDACTED]

SAEs that occur after the Safety Follow-up Visit and are considered related to study drug(s) will be recorded on the Vertex Clinical Trial Safety Information Collection Form (hereafter referred to as the “SAE Form”) using a recognized medical term or diagnosis that accurately reflects the event. SAEs will be assessed by the investigator for relationship to the investigational study drug(s) and possible etiologies. On the SAE Form, relationship to study drug(s) will be assessed only as related (includes possibly related) or not related (includes unlikely related), and severity assessment will not be required. For the purposes of study analysis, if the event has not resolved at the end of the study reporting period, it will be documented as ongoing. For purposes of regulatory safety monitoring, the investigator is required to follow the event to resolution and report the outcome to Vertex using the SAE Form.

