## 9 STATISTICAL ANALYSIS

### 9.1 General Considerations

Data from Part A and Part B will be analyzed separately.

The Schedule of Assessments is provided in Section 3 of the CSP. The precision standards for reporting safety and efficacy variables are provided in an internal Biometrics document that specifies the programming rules including the precision for derived variables.

**Continuous variables** will be summarized using the following descriptive summary statistics: the number of subjects (n), mean, standard deviation (SD), median, minimum value (min), and maximum value (max).

**Categorical variables** will be summarized using counts and percentages. Percentages will be presented to 1 decimal place.

**Baseline** unless otherwise specified, is defined as the most recent non-missing measurement (scheduled or unscheduled) collected prior to the first dose of study drug in the corresponding Part.

Note: in Part B, for subjects who take CFTR modulators (e.g., Orkambi) during the 28 days before the screening visit, the data collected at the screening visit will not be used for baseline derivation for sweat chloride and LCI.

**Absolute change** from baseline will be calculated as Post-baseline value – Baseline value.

**Relative change** from baseline will be calculated and expressed in percentage as 100% × (Post-baseline value – Baseline value) / Baseline value.

**Treatment-emergent (TE) Period** for Part A and Part B will include the time from the first dose of study drug in the corresponding Part through 28 days after the last dose or the completion of study participation date in the corresponding Part, whichever occurs first. Refer to Section 9.1.6 of the CSP for the definition of completion of study participation.

**Unscheduled visits:** Unscheduled visit measurements will be included in analysis as follows:

- In scheduled visit windows per specified visit windowing rules
- In the derivation of baseline and last on-treatment measurements
- In the derivation of maximum and minimum values during TE periods, and maximum and minimum change from baseline values during TE periods for safety analyses
- In individual subject data listings as appropriate

**Visit windowing rules** for protocol-defined visits in Part A are provided in [Appendix A](#).

**Incomplete/missing data** will not be imputed, unless specified otherwise.

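### For Part B children who stop drug early but stay in the study, Section 13.1.1.3 can end AE collection up to 7 days before the treatment-emergent period ends, in conflict with Table 3-4

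*Protocol*

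**What the plan says.** Four parts of the plan bear on when AE collection ends for a Part B child who stops study drug early without withdrawing consent.

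- **Protocol 13.1.1.3 (AE documentation).** Where there is a Safety Follow-up Visit, the rule is: "For enrolled subjects who have a Safety Follow-up Visit: through the Safety Follow-up Visit". Where there is none, collection ends at the earlier of 28 days after the last dose or "the ETT Visit, if that visit is 3 weeks or later following the last dose of study drug". The same section also has parents asked about AEs at every study visit.
- **Protocol Table 3-4 and 9.1.6.** The AE row of the schedule reads "Continuous, From Signing of ICF Through Completion of Study Participation". For early stoppers, Section 9.1.6 defines that date as "the latest of the Week 24 Visit, ETT Visit, or Safety Follow-up Visit (if required". Sections 9.1.2 and 9.1.4 keep these children in all scheduled visits. Section 11.5.4 has clinically significant ECG abnormalities recorded as AEs up to the same completion date.
- **Visit timing, Protocol 9.1.3 and 9.1.4.** "The Safety Follow-up Visit is scheduled to occur 28 (± 7) days after the last dose of study drug". If the ETT Visit comes 3 weeks or more after the last dose, "then the ETT Visit will replace the Safety Follow-up Visit".
- **TE period, Protocol 12.3.1 and SAP 9.1.** It runs from first dose "through 28 days after the last dose or the completion of study participation date", whichever comes first.

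For SAEs, Protocol 13.1.2.2 requires reporting regardless of causality for "All SAEs that occur after obtaining informed consent through the Safety Follow-up Visit". After that visit, only SAEs considered related to study drug are reported.

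**The concern.** Two end dates for AE collection apply to the same child. Section 13.1.1.3 stops at a visit about four weeks after the last dose, while Table 3-4 continues to Week 24 or beyond. The AE row of Table 3-4 refers the reader both to Section 13.1 and to the completion date in Section 9.1.6, so one row points to both answers.

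Most of the disputed time lies after the TE period and affects listings only. One stretch does not. When the visit that closes collection falls on days 21 to 27 after the last dose, completion of participation is usually still Week 24, so the TE period runs on to day 28. Its last days then count in the analysis but lie outside the Section 13.1.1.3 collection window.

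AEs are one component of the Part B primary safety endpoint. Early stoppers may include children who stopped for tolerability. In a single-arm study of about 70 children, AE capture in this group should not depend on which section a site follows. Unrelated SAEs at the continued visits are under the same conflict.

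**Working it through.** **Inputs**

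- Safety Follow-up Visit: 28 ± 7 days after last dose (Protocol 9.1.3), so 28 − 7 = day 21 to 28 + 7 = day 35.
- Late ETT Visit: from 3 weeks, 3 × 7 = day 21 (Protocol 9.1.4 and 13.1.1.3).
- Week 24: target study day 169 (SAP Table 12-2), ± 5 days (Protocol Table 3-4), so 164 to 174.
- Dropout: 10% or 20% of 70 (Protocol 12.1). 70 × 0.10 = 7 and 70 × 0.20 = 14, leaving 63 and 56, as the plan states.

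**Formulas.** Let L be the study day of the last dose, s the days from last dose to the Safety Follow-up Visit (or the late ETT Visit that replaces it), and W the Week 24 study day.

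- AE cut-off under 13.1.1.3 = L + s
- Completion under 9.1.6 = max(W, L + s)
- TE end = min(L + 28, completion)
- TE days not collected = TE end − cut-off, or 0 if negative
- Days in conflict with Table 3-4 = completion − cut-off

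**Results with s = 21 and W = 169**

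| Last dose (L) | Cut-off | TE end | Completion | TE days not collected | Days in conflict with Table 3-4 |
|---|---|---|---|---|---|
| 1 | 22 | 29 | 169 | 7 | 147 |
| 29 | 50 | 57 | 169 | 7 | 119 |
| 85 | 106 | 113 | 169 | 7 | 63 |
| 113 | 134 | 141 | 169 | 7 | 35 |
| 141 | 162 | 169 | 169 | 7 | 7 |
| 142 | 163 | 169 | 169 | 6 | 6 |
| 147 | 168 | 169 | 169 | 1 | 1 |
| 148 | 169 | 169 | 169 | 0 | 0 |

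The largest gap is 28 − 21 = 7 days, which is 7/28 = 25% of the post-dose TE days for that child. From day 142 the completion date caps the TE period and the gap shrinks. It is gone by day 148.

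**Varying the visit day (L = 29, W = 169)**

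| s | TE days not collected | Days in conflict with Table 3-4 |
|---|---|---|
| 21 | 7 | 119 |
| 24 | 4 | 116 |
| 28 | 0 | 112 |
| 35 | 0 | 105 |

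**Varying Week 24 (s = 21).** With W = 164 the full 7-day gap holds for a last dose up to day 136, and some gap remains up to day 142. With W = 174 the limits are day 146 and day 152.

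**Groups without a TE gap.** For Part B treatment completers who do not enter the extension study, participation ends at the Safety Follow-up Visit, so the TE period cannot outlast collection. In Part A, completion for early stoppers is the latest of Day 15, ETT or Safety Follow-up. The same formulas with Day 15 in place of W give 0 for every last-dose day from 1 to 15.

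**The case against.** The strongest reply is that nothing need be lost. Table 3-4 requires collection to completion, and Section 13.1.1.3 itself has AEs asked about at each visit and recorded in the CRF for all enrolled children. A TE gap arises only when completion falls after the closing visit, so at least one later scheduled visit, Week 24, always remains. A site following Table 3-4 has no gap. This stands, and it makes the finding conditional: the text gives sites contradictory instructions, but does not show that data will be missing. It does not remove the conflict, because Section 13.1.1.3 states an explicit end to collection.

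Other limits also stand.

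- **Timing.** At the nominal day-28 follow-up the gap is zero. Section 9.1.4 wants the ETT Visit promptly, so a late ETT Visit should be the exception.
- **Analysis.** Part B safety analyses use TE-period data (SAP 9.4.2) and AE summary tables cover TEAEs only (Protocol 12.3.4.1). AEs after day 28 are only listed, so the weeks of conflict up to Week 24 do not touch the TEAE summaries.
- **SAEs.** A reader might infer that SAE reporting stops altogether at the Safety Follow-up Visit. It does not: related SAEs are still reported afterwards under Section 13.1.2.2. Only unrelated SAEs fall under conflicting rules.
- **Numbers.** A reader might take the 7 to 14 expected dropouts as the number affected. The documents do not support that. The affected children must stop drug, stay in the study, have the closing visit on days 21 to 27 and stop early enough. No rate is given for any of these conditions, and children who withdraw consent or are lost to follow-up have earlier completion dates under Section 9.1.6.

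**Conclusion.** The inconsistency is real and holds for Part B children who stop drug early and remain in the study. If a site applies the Section 13.1.1.3 cut-off and the Safety Follow-up or late ETT Visit falls on days 21 to 27, 1 to 7 of the 28 post-dose TE days go uncollected. With Week 24 on study day 169 and a day-21 visit, this requires a last dose before about study day 148; the limit moves by 5 days either way with the Week 24 window. The size per child follows from date arithmetic alone. The number of children cannot be derived from the documents, and 7 to 14 is only a ceiling.

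The conflict with Table 3-4 is wider, since it persists when the follow-up visit is on day 28 or later, but there it bears on listings and on the reporting of unrelated SAEs, not on TEAE counts. The point deserves correction because safety is the primary objective and the remedy is cheap. It does not undermine the safety analysis as a whole.

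**What to change.** Reconcile Sections 13.1.1.3 and 13.1.2.2 with Table 3-4. State that, for subjects who discontinue treatment early and remain in the study, AEs are collected and SAEs reported regardless of causality through completion of study participation as defined in Section 9.1.6. Because the TE period can never extend past completion, this brings the gap to 0 for every last-dose day.

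Leave the existing end dates unchanged for treatment completers, children entering the extension study and those who withdraw consent. A blanket minimum of 28 days for everyone should not be added. After consent is withdrawn no further assessments are made (Section 9.1.4). For completers with an early Safety Follow-up Visit, a minimum would require an unscheduled contact although they have no TE gap.

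The cost is a wording change and slightly more AE recording at visits already scheduled. The TE definition in SAP 9.1 can stay as it is.
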